9.4 PHI Documentation

PHI will be recorded for potential participants prior to obtaining informed permission/assent/consent during pre-screening procedures outlined above. This information will be stored securely on the Hospital Share Drive under the file name "Potential Participant Log." (see Supplementary Documents, under "U54 Potential Participant Log.") The PHI collected will consist of:

- Patient first and last name
- Appointment date and appointment location (PCC or ADHD Clinic)
- Parent Name
- Parent Phone Number

Other non-PHI collected on this spreadsheet will include attempts to call the family including date, time, notes from the conversation, interest, if consent form was sent, follow-up call attempts after consent form was sent, and enrollment status. This spreadsheet of potential participants will only be kept until completion of enrollment to avoid duplicate recruitment.

A partial waiver of HIPAA Authorization (waiver for recruitment purposes only) was approved at the time of the initial protocol approval (see Notification of Initial Approval, 11/29/2016).

Data for participants who are determined to be ineligible for the study after enrollment/upon screening will be stored in the "U54 Master Enrollment Log" and will be documented as "screen fails." (see Supplementary Documents, under "U54

Master Enrollment Log"). The reason for screen fail will also be documented in the participant's study binder.

## 10.0 Study Timelines

### 10.1 Study Duration

[figure not shown]
- The duration of an individual subject's participation in the study will be approximately 6-8 months.
- The duration anticipated to enroll all subjects and complete participant study procedures is approximately 5 years (June 2022)
- The estimated date for the investigators to complete this study (complete primary analysis) is approximately 5 years from when enrollment began (December 2022).

## 11.0 Procedures Involved

### 11.1 Study Design Overview

This is a longitudinal exposure escalation study of atomoxetine in children with ADHD. This study simultaneously measures participants' pharmacokinetic and pharmacodynamic profiles after administration of a single-dose of ATX, approximately 2-8 weeks, and approximately 18 weeks of chronic use as well as the therapeutic efficacy/clinical response after chronic use. The study design is best illustrated by categorizing the chronological visits by phase as illustrated in Figure 4. The phases occur in the following order:

- 1) Prescreen
- 2) Enrollment
- 3) Screen
- 4) Intervention

**Fig. 4 – Study Design Overview**

1. Prescreen

This phase consists of identifying and contacting eligible study participants and presenting the study opportunity. See section 9.0 for details.

After a family expresses interest in enrolling, study personnel will contact the participant/family to review key parts of the study in preparation for the first research visit. See Appendix F “Study Coordinator/Research Assistant Scheduling Script” for details. This discussion will review:

- a. Frequency and duration of study visits
- b. If a medication washout is required, explanation about washout safety and instruction to not begin the washout until written permission/assent or consent has been obtained
- c. The study drug is only available in capsule form, so the child will need to be able to swallow pills
- d. The study will require multiple blood draws and an IV

2. Enrollment

Enrollment typically takes place during Research Visit 1 Part 1. Enrollment can occur prior to Research Visit 1 Part 1 when a diagnosis of ADHD has not been established or the diagnosis cannot be verified by review of EMR. Additionally, enrollment may occur prior to Research Visit 1 Part 1 by phone or telehealth to minimize in-person procedures to prevent SARS-CoV-2 viral transmission. Research Visit 1 Part 1 visit takes place in the PCRU and includes obtaining informed consent or permission/assent, gathering information about a participant’s comfort with needlesticks and pill swallowing, obtaining a blood sample to determine the participant’s genotype, collecting medical history, demographics, medication history, and initiating an ADHD medication washout if needed.

3. Screen

After enrollment at Research Visit 1 Part 1, the remaining screening procedures will occur during Research Visit 1 Part 2 and the Intake Visit with Study Physician.

If study personnel determine no washout will be required, Research Visit 1 Parts 1 and 2 may occur in tandem. However, if a washout will be required, the 2 parts of Research Visit 1 will occur separately. After the participant has completed the washout, he or she will return for Part 2 to initiate screening procedures.

Research Visit 1 Part 2 takes place in the PCRU and includes obtaining baseline research psychometric measures and baseline safety and research measures to assess for inclusion/exclusion criteria. Psychometric measures will be administered via paper questionnaires, electronically (as with K-SADS-COMP), or obtained using the Comprehensive Health and Decision Information System (CHADIS). K-SADS-COMP was

developed using Microsoft ASP.NET 4.0 framework and Microsoft SQL Server 2016 database. These platforms are stable, reliable and secure. CHADIS is a secure web-based patient questionnaire tool to assist healthcare professionals with their patient clinical care decisions. Parents and caregivers of the study participant are able to complete certain questionnaires online. These results are then imported into the participant's electronic medical record.

The Intake Visit with Study Physician takes place in the Developmental and Behavioral Health Sciences Clinic at the Adele Hall campus, the ADHD Clinic on College Boulevard, or via telehealth. During this visit, the participant and family undergo a routine standard of care visit with a study physician to confirm/infer a diagnosis of ADHD, determine an ADHD subtype, assess for co-morbidities, perform a physical exam, and determine if ATX is an appropriate therapy for the participant. If the Intake Visit occurs via telehealth, all in-person procedures may be omitted. Further details are described in section 11.2. The results from questionnaires will be reviewed. For participants without a formal diagnosis (i.e. documented on participant's electronic medical record), questionnaires must be received from both parent and teacher.

If the subject was seen by a study physician within 6 weeks prior to enrollment and at baseline (meaning not taking any ADHD medication), the visit does not need to be repeated in its entirety. The study physician may amend his or her visit note in the EMR to document the following for research purposes:

- a. Confirm/infer ADHD diagnosis
- b. Assess and confirm/infer diagnosis of other comorbidities
- c. Assess and confirm appropriateness of atomoxetine therapy for participant
- d. Complete Clinical Global Impression (CGI).

After this, the Principle Investigator(s) (PI) will review information from these visits to determine if the participant meets all eligibility criteria.

4. *Intervention assignment*

Once all inclusion and exclusion criteria have been assessed during screening procedures, the PI will document that the subject meets all eligibility criteria to qualify for study participation. The PI will then assign the participant to one of three study designs based on his or her CYP2D6 activity score (see section 5.1). The length and data collection procedures of Research Visit 2, Research Visit 3, and Research Visit 4 will vary based on the participant's CYP2D6 activity score, genotype, and frequency of dosing. During the course of the study following Research Visit 2, some study participants may be changed from the usual once daily dosing to twice a day (bid) dosing per their study physician. These participants initially assigned to Study Design 2 may require switching to Study Design 3 as determined by the research team to capture pharmacokinetic data

of non-Q12-hour bid dosing. Additionally, Study Design 3 participants taking twice daily dosing may be switched back to daily dosing over the course of the study, thus necessitating assignment back to Study Design 2. Given the decreased drug clearance of poor metabolizers, participants in Study Design 1 are not anticipated to be prescribed bid dosing and thus would not require switching to Study Design 3. These length variations are illustrated in Figure 5 below. Data collection procedure variations are illustrated in the specific visit descriptions in section 11.2.

Visit Length by Study Design			
	Study Design 1 Activity Score < 1 or participants have 2 reduced function alleles	Study Design 2 Activity Score $\geq$ 1 (i.e. all other scores)	Study Design 3 Participant previously in Study Design 2, on non-Q12-hour bid dosing
Research Visit 2	72 Hours	12 Hours	Non applicable
Research Visit 3	24 Hours	12 Hours	Up to 24 Hours
Research Visit 4	24 Hours	12 Hours	Up to 24 Hours

**Figure 5** – Please note, visit length is expressed in hours post-drug administration.

After study design assignment, the participant will begin the study intervention procedures, starting with Research Visit 2. See below for a brief description of each visit.

**Research Visit 2** – This visit is also referred to as pharmacokinetic study 1 (PK1), or first dose PK. This visit takes place in the PCRU and also includes procedures occurring in preparation of this visit, in addition to procedures occurring after administration of the first dose of ATX.

**Research Visit 3** – This visit is also referred to as pharmacokinetic study 2 (PK2) or steady state PK. This visit takes place in the PCRU and also includes procedures occurring in preparation of this visit, in addition to procedures after administration of medication when the participant is at steady-state. Steady-state is assumed to have been achieved once the participant has been taking atomoxetine routinely for two weeks. This visit may occur any time after the participant has been taking study drug routinely for 2 weeks and prior to the 18-Week Visit with Study Physician. If the participant is prescribed non-Q12-hour twice daily dosing at this time, the study team will notify participant and/or family prior to visit, and the participant will be switched to Study Design 3 for this research visit. Compliance will be documented by checking the capsule count against the medication calendar and documented in corresponding CRFs. Additionally, study personnel will reach out participants and/or their families ~1 week

prior to remind them that all medications need to be taken in the week prior to Research Visit 3. Study personnel will call prior to Research Visit 3 to ensure that participants have been compliant for a week.

6-Week Visit with Study Physician – The participant and family meet with a study physician approximately 6 weeks after ATX therapy was initiated. A ± 2-week window is allowed for ease of scheduling and to ensure Research Visit 3 occurs prior to the visit. Prior to this visit, questionnaires will be sent out via CHADIS to parents and teachers to assess participant's behavior. During this visit, safety, efficacy, and side effects will al be assessed and dose adjustments will be made accordingly. Dose adjustments may be outside research and visits with study physicians as needed.

12-Week Visit with Study Physician – The participant and family meet with a study physician approximately 6 weeks after the 6-Week Visit with Study Physician. A ± 2-week window is allowed for ease of scheduling. Prior to this visit, questionnaires will be sent out via CHADIS to parents and teachers to assess participant's behavior. During this visit, safety, efficacy, and side effects will be assessed and dose adjustments will be made accordingly. Dose adjustments may be outside research and visits with study physicians as needed.

18-Week Visit with Study Physician – The participant and family meet with a study physician approximately 6 weeks after the 12-Week Visit with Study Physician. A ± 2-week window is allowed for ease of scheduling. Prior to this visit, questionnaires will be sent out via CHADIS to parents and teachers to assess participant's behavior. During this visit, safety, efficacy, and side effects will be assessed and dose adjustments will be made accordingly. In addition, baseline questionnaires will be re-administered to gauge symptom and impairment changes post-treatment initiation. Dose adjustments may be outside research and visits with study physicians as needed.

Research Visit 4 – This visit is also referred to as pharmacokinetic study 3 (PK3) or end of study PK. This vist occurs after the 18-Week Visit with Study Physician. This visit takes place in the PCRU and consists of the same procedures as Research Visit 3. Determination of Study Design will be confirmed prior to visit, as some participants may require switching to a different study design if frequency of dosing has changed. During this visit, baseline psychometric measures will be re-administered to measure change post-treatment initiation. An end of study EKG will be obtained, and a Dietary Survey Questionnaire will be administered.

- Description of Research Procedures

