## 4.0 Study Endpoints and Rationale

### 4.1 Primary Study Endpoints

The primary aims of this study focus on characterizing the relationship between changes in pharmacodynamic markers and clinical outcome measures, when inter-subject variability in ATX pharmacokinetics has been minimized (Fig. 3). ATX pharmacodynamics will be measured using plasma DHPG and metabolomic data, pupillometry during attention tasks, and changes in blood pressure and heart rate. Clinical outcomes will be assessed by standardized ADHD measures used in a clinical setting, of which include: NICHQ Vanderbilt Assessment Scale (ADHD symptom rating scale); Strengths and Difficulties Questionnaire; Child Behavior Checklist; the School Intervention Questionnaire; Medication Side Effects; and Clinical Global Impression. Some of these questionnaires will also capture comorbidity information, such as Oppositional Defiant Disorder (ODD). We will also use the Kiddie Schedule for Affective Disorders and Schizophrenia for School-Age Children – Present and Lifetime Version (K-SADS-PL) or K-SADS-COMP (the computerized version of the K-SADS-PL) to diagnose ADHD and commonly associated comorbidities. The K-SADS-PL is a semi-structured interview that is extensively used in clinical psychology research to diagnose an extensive array of psychopathology based on the DSM-5. Given the length of this interview, common research practices are to select only the modules that are expected to be pertinent to the study participant (Black et al., 2012; Kariuki et al., 2018; Caudle et al., 2020). The K-SADS-PL modules selected for this research study are as follows: agoraphobia, separation anxiety disorder, social anxiety disorder/selective mutism, specific phobias, generalized anxiety, obsessive compulsive disorder, and post-traumatic stress disorder. The other research comorbidities or impairments that we will assess for and associated psychometric tests we will use are as follows: impairment in executive function using the Behavior Rating Inventory of Executive Function (BRIEF); anxiety using the Screen for Child Anxiety and Related Disorders (SCARED); intelligence quotient using the Kaufman Brief IQ Test (KBIT); and sluggish cognitive tempo using the Barkley Sluggish Cognitive Tempo Scale (SCT). Pharmacodynamic data will be obtained: baseline (Research Visit 1); when ATX is first initiated in a participant with the first dose (Research Visit 2); when the participant has taken the medication chronically and thus, expected to be at steady-state (Research Visit 3); and at the end of study when the dose has been optimized for the participant (Research Visit 4). Concurrent pharmacokinetic analysis will take place to ensure that ATX plasma and urine exposure variability has been minimized using methods described in a previous ATX pharmacokinetic study conducted at Children's Mercy Hospital (Brown et al., 2016). Additionally, we will measure ATX and metabolites in sweat as surrogate for fraction of drug unbound (Marchei et al., 2012; Marchei et al., 2013). The clinical ADHD questionnaires will be administered at the Intake Visit and at follow-up visits following initiation of atomoxetine treatment (6-weeks, 12-weeks, and

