## 5.2 Drug Handling

The study drug, ATX, will be stored, prepared, labeled, and dispensed by the CMH Investigational Drug Service (IDS) pharmacy. Study file documentation, accountability, and records for dispensing of atomoxetine will be maintained by IDS pharmacy personnel.

The study physician will submit a signed and dated prescription for ATX to IDS Pharmacy. Alternately, designated study personnel will deliver a prescription that has been signed and dated prescription by the study physician to IDS Pharmacy. A copy of all prescriptions will be retained in the participant's study binder. IDS Pharmacy will deliver the ATX prescription to the PCRU for Research Visit 2. Subsequent prescriptions for ATX will be filled as needed and will typically occur in conjunction with 6-week, 12-week, and 18-week visits. Medication refills may also occur outside of the 6-week, 12-week, and 18-week visits. Medication refills may be handed off or delivered to the participant to reduce foot traffic at Children's Mercy Hospital, as needed. Dose adjustments may also occur outside of the 6-week, 12-week, and 18-week visits.

All investigational drug will be returned to the study team at the end of the study for disposal by the IDS pharmacy, unless the child and their family would like to continue using ATX. In addition, if the participant would like to discontinue the study drug, but he or she will require an ATX wean to reduce risk of side effects from abrupt discontinuation as directed by his or her study physician, the participant may keep the remaining drug to complete this wean.

Refer to the Investigational Drug Service Policy and Procedure (Last Revision 04/2020) for the standard operating procedure (SOP) outlining details regarding the control of the study drug used in this protocol. Transportation of study drug will be handled by both IDS pharmacy and study personnel. Refer to the Investigational Drug Product Transport Policy (Last Revision 12/2019.) The locations of drug transportation and how this will be conducted are summarized below. Further details for drug handling may be found in Appendix J, "Study Drug Timeline."

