- iii. Remind participant to bring U54 Study Booklet, which contains the participant’s medication calendar (in-person visit only).

*Day of Visit*

- a. This visit may occur in-person or via telehealth, at the Study Physician’s discretion.
- b. If this visit occurs in-person:
  - i. Conduct physical exam. Documentation will be in EMR.
  - ii. Assess ADHD symptoms/review questionnaires.
  - iii. Assess other comorbidities and concurrent medications. Add to Concomitant and Prior Medications Log.
  - iv. Assess for atomoxetine side effects.
  - v. Make atomoxetine dose changes as necessary, with guidance from study team if necessary and document reason for changes.
  - vi. Document prescription change (if made) in CRF.
  - vii. Assess for adverse events. Document in Adverse Events log.
  - viii. Verify medication calendar with remaining capsules count.
  - ix. Make copies of pages in medication calendar.
  - x. Complete Clinical Global Impression (CGI)
- c. If this visit occurs via telehealth, proceed with all procedures stated above with the following exceptions:
  - i. The physical exam will be omitted.

- ii.* Ask the participant to email pictures of the pertinent adherence calendar pages and a picture of the remaining medication.

*Other Visit Related Activities*

- a.* Obtain a signed and dated prescription for atomoxetine from Study Physician. This may occur prior, during, or after this visit.
      - b.* Submit signed and dated prescription to Children's Mercy Hospital Investigation Drug Services (IDS) pharmacy.
      - c.* Deliver medication to patient, or leave medication at Children's Mercy Outpatient Pharmacy for family to pick up medication at their convenience. Medication may be mailed (see section 5.2) at the request of the participant's family.
      - d.* Add compensation to participant's Greenphire account if calendar and medication bottle brought to visit.
      - e.* If Children's Mercy Hospital develops procedures for drive-up collection of vital signs (e.g. heart rate, blood pressure), the Study Physician may ask the participant to use this service to supplement their evaluation.

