**See the Schedule of Events (SOE) table below outlining all of the above procedures by visit.**

SHORT TITLE: ATX-PBPK-PD-Clinical Outcomes (U54)

Schedule of Events	Prescreen	Research Visit 1* θ	Intake with Study Physician ψ	Research Visit 2*	Research Visit 3*	6-Week Visit with Study Physician ψ	12-Week Visit with Study Physician ψ	18-Week Visit with Study Physician ψ	Research Visit 4*	2-week Post-Study Check
Time point	N/A	N/A	N/A	Start Med/Day 0	Day 0 + at least 2 weeks ε	Day 0 + 6 weeks and after RV3	6-Week Visit with Study Physician + 6 weeks	12-Week Visit with Study Physician + 6 weeks	After 18-Week Visit	After Research Visit 4
Visit Window	N/A	N/A	N/A	N/A	See note €	± 2 weeks	± 2 weeks	± 2 weeks	N/A	± 1 weeks
Type of Visit/Event	Phone	Phone/In Person	In person/telehealth	In Person	In Person	In person/telehealth	In person/telehealth	In person/telehealth	In Person	Phone
Potential Participant Identified	X									
Introduce the Study	X									
Schedule Research Visit 1	X									
Obtain Consent or Permission/Accent		X 								
Obtain participant continued assent (verbal)				X	X				X	
Document continued assent in research note				X	X				X	
Provide U54 Study Booklet		X								

SHORT TITLE: ATX-PBPK-PD-Clinical Outcomes (U54)

Schedule of Events	Prescreen	Research Visit 1* θ	Intake with Study Physician ψ	Research Visit 2*	Research Visit 3*	6-Week Visit with Study Physician ψ	12-Week Visit with Study Physician ψ	18-Week Visit with Study Physician ψ	Research Visit 4*	2-week Post-Study Check
Needlestick/Pill Swallowing Questions		X								
Explain and Begin Washout (if needed)		X								
Demographic Data		X								
Prior/Concomitant Meds		X		X	X	X	X	X	X	
Prior Medical History		X								
Vital Signs		X		X 	X 				X 	
Physical Exam		X	X	X	X	X	X	X	X	
Electrocardiogram		X							X	
Tanner Staging (optional)		X		X	X				X	
Pregnancy Test		X		X	X				X	
Safety Laboratory Tests (CBC w/diff; Base Met; LFTs; UA w/micro)		X		X	X				X	
Confirm ADHD Diagnosis			X							
Assess for Comorbidities			X			X	X	X		

SHORT TITLE: ATX-PBPK-PD-Clinical Outcomes (U54)

Confirm ATX appropriateness for participant			X							

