ψThese visits will occur at either the ADHD Clinic on College Boulevard or in the Developmental and Behavioral Sciences Clinic. If these visits are telehealth visits, all in-person procedures, such as obtaining vitals or a physical exam, may be omitted.

This visit can occur in two parts to minimize time of washout.

€The window for this visit is flexible and has been expanded from the previous versions of this protocol. This visit can occur anytime after the participant has been taking medication regularly for 2 weeks and up until prior to the 18-Week Visit with Study Physician.

○ Procedures to Reduce Risks

1. Medical Chart Review during Prescreen will be used to determine if a potential participant has any of the following:
  - a. Diagnosis or indication of underlying risk for cardiotoxicity, such as presentation of structural cardiac abnormalities, cardiomyopathy, or arrhythmias.
  - b. Diagnosis or indication of disease that may cause abnormal absorption or gastric emptying.
  - c. Previous history or indication of prior adverse drug reaction to atomoxetine
  - d. Concurrent therapy with drugs known to inhibit CYP2D6 or previous treatment with strong CYP2D6 inhibitors.
  - e. Concurrent therapy with other psychiatric/behavioral drugs
2. The two parts of Research Visit 1 may occur at separate times for participants who require a washout prior to beginning atomoxetine therapy. Research Visit 1 Part 1 includes a blood stick for genotyping purposes. Genotyping analysis, which takes approximately one week to complete and interpret, will be conducted while the participant is washing out. Were we to collect genotyping sample when the participant is at baseline, the participant could potentially be off of medication for ~ 2 weeks, while waiting for genotyping results such that ATX can be dosed in the participant using the iGO-PK model.
3. Needlestic comfort and pill-swallowing ability questions will be asked to reduce discomfort and anxiety associated with needlessticks and taking the study drug.
4. Baseline electrocardiogram during Research Visit 1 to assess presence of any underlying risks for cardiotoxicity prior to starting participant on ATX.
5. End of study electrocardiogram during Research Visit 4 to assess for any cardiac injury that may have occurred while the participant was taking ATX chronically.

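### The two-week steady-state rule counts time on atomoxetine, not time on the current dose, so a slow metaboliser's profile taken soon after a dose step could be tabulated as steady state

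*Combined protocol and SAP*

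**What the plan says.** Section 11.1, Research Visit 3: "Steady-state is assumed to have been achieved once the participant has been taking atomoxetine routinely for two weeks". The Schedule of Events footnote has the same rule, "This visit can occur anytime after the participant has been taking medication regularly for 2 weeks", and lets RV3 fall as late as just before the 18-Week Visit.

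Dose changes are widely allowed. Section 5.1 sets targets of 400, 600 and 800 ng/mL and permits a slow initial titration. Section 5.2 adds: "Dose adjustments may also occur outside of the 6-week, 12-week, and 18-week visits". At the physician visits the instruction in section 11.2 is: "Make atomoxetine dose changes as necessary, with guidance from study team if necessary and document reason for changes".

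RV4 has no minimum gap after the last dose review: "This vist occurs after the 18-Week Visit with Study Physician" (section 11.1). It repeats the procedures of RV3.

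The checks before RV3 and RV4 (section 11.2) cover one week of adherence and, through the study design assignment, dosing frequency. Section 20.1 then derives Cmax,ss, AUC0-tau,ss and related parameters from data after chronic dosing to steady state. Neither that text nor the definition of the pharmacokinetic population sets a dose-stability condition.

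Some text points the other way. The 6-Week Visit window exists partly "to ensure Research Visit 3 occurs prior to the visit", and the Schedule of Events times that visit at "Day 0 + 6 weeks and after RV3". Section 4.1 places RV4 "at the end of study when the dose has been optimized for the participant".

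**The concern.** Accumulation starts again at each dose step. A child on atomoxetine for ten weeks, with a dose raised two days before the visit and every prescribed capsule taken, meets the two-week rule and passes every pre-visit check. In a slow metaboliser that profile lies between the old and the new steady state: too low for the recorded dose after an increase, too high after a decrease.

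At stake are the steady-state PK tables and any judgement of whether the target Cmax,ss was reached. Section 4.1 relies on concurrent PK analysis to show that exposure variability has been minimised, and a mislabelled profile would look off target when only time was lacking.

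**Working it through.** **Inputs from the documents.** Steady state assumed at 14 days (section 11.1); targets 400, 600 and 800 ng/mL (section 5.1); once-daily dosing as the usual regimen (section 11.1).

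**Assumptions.** The documents give no half-life or absorption rate for atomoxetine. They do show that slow removal is expected in some children: the washout table in section 11.2 gives 2-4 weeks for atomoxetine, depending on CYP2D6 genotype, and Study Design 1 samples RV2 to 72 h. I take half-lives h of 5, 12, 24 and 48 h, exposure proportional to dose, and one compartment.

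**The plan's own figure.** Two weeks cannot be derived from the documents, but it can be checked. At a constant dose the fraction of steady state reached is 1 - 2^(-336/h). At h = 48 this is 1 - 2^(-7) = 99.2%. Five half-lives fit into 14 days for any h up to 336/5 = 67 h. With an unchanged dose the rule is ample.

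**After a dose step.** At the m-th new once-daily dose,

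AUCtau = AUC(new,ss) × [1 - 2^(-24m/h)] + AUC(old,ss) × 2^(-24m/h),

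so the relative shortfall is (1 - Dold/Dnew) × 2^(-24m/h). For 400 to 600 the first factor is 1/3.

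| Assumed h | 1st new dose | 2nd | 3rd |
|---|---|---|---|
| 5 h | 1.2% | <0.1% | <0.1% |
| 12 h | 8.3% | 2.1% | 0.5% |
| 24 h | 16.7% | 8.3% | 4.2% |
| 48 h | 23.6% | 16.7% | 11.8% |

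At 48 h the fifth new dose is still (1/3) × 2^(-2.5) = 5.9% short.

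For a reduction from 600 to 400 the first factor is 1 - 1.5 = -0.5. At h = 24, AUCtau is 25%, 12.5% and 6.25% too high at the first three new doses.

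**Peaks.** Superposition with first-order absorption (ka 0.5 to 2 per hour, h = 24), scaled to a new steady-state peak of 600 ng/mL, gives 494-499, 547-549 and 574-575 ng/mL at the first three new doses. That is 17-18%, 8-9% and 4% short, close to the AUC figures.

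**The case against.** The strongest reply is that the plan never orders such a profile into the table. Section 20.1 speaks of data after dosing to steady state, and section 11.1 requires routine intake, which the first days of a new dose fit poorly. This stands in part. A reader might infer that these profiles would certainly be tabulated; the text supports only that they could be, because the sole operational definition is two weeks on drug.

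Second, the rule is written for RV3. Section 1.0 labels RV4 the end-of-study PK visit, and section 4.1 intends an optimised dose by then. This also stands: the rule reaches RV4 only through the repeated RV3 procedures and the steady-state table. Yet a dose changed at week 18 may be the optimised one and still not be at steady state.

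Third, RV3 is expected at about 2-8 weeks and usually before the 6-Week Visit, and staff who prepare prescriptions can see a recent change. That lowers the frequency. It does not close the gap, since later visits and earlier dose changes are allowed and no rule says to reschedule.

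Fourth, section 20.1 specifies no formal comparison of achieved with targeted Cmax,ss, and doses are rounded to available capsules anyway. This limits the consequence but does not remove it, given section 4.1's reliance on concurrent PK.

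Fifth, the one-compartment arithmetic is simpler than the models in section 5.1, which use two compartments for non-poor metabolisers and a secondary peak for poor metabolisers. The figures are therefore indicative.

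Finally, doses change for poor response or side effects, so dropping these profiles would select on outcome-related factors. That is a good reason to flag them and not exclude them.

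**Conclusion.** The gap is real and minor. The rule can label as steady state a profile that is not, for a slow metaboliser within a few days of a dose step. For a 400-to-600 step and half-lives of 24 to 48 h, AUCtau is about 17-24% short at the first new dose and 4-12% at the third; at 5 h the error is about 1%. These sizes rest on assumed half-lives, once-daily dosing and a simple model. How often a step falls this close to a visit cannot be estimated from the documents; given the usual visit order and the optimised dose intended at RV4, it is probably a minority of profiles.

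Two stronger readings are not supported. One is that two weeks is too short for poor metabolisers; at a constant dose it is ample. The other is that the main hypotheses are biased. The observed values are still the exposure the child had that day, so the SLC6A2 hypothesis and the concentration-driven DHPG model are not directly affected. I claim no effect on the iGO-PK model or on CL/Fss as section 20.1 writes it.

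**What to change.** In section 20.1, define steady state as at least two weeks of routine dosing, with dose and frequency unchanged for at least five of the child's RV2 half-lives. Where that half-life cannot be estimated (section 20.1 foresees too few post-peak points, and Study Design 2 samples only to 12 h), use 14 days in Study Design 1 and about 3 days in Study Design 2.

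Error left after a 400-to-600 step:
- five half-lives: (1/3) × 2^(-5) = 1.0%
- 14 days at h = 48: (1/3) × 2^(-7) = 0.3%
- 3 days at h = 12: (1/3) × 2^(-6) = 0.5%

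Flag RV3 and RV4 profiles that do not meet the definition, summarise the steady-state parameters with and without them, and analyse the flagged profiles with the recorded dosing history.

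The cost is SAP wording. Dose changes are already documented, and RV2 is already sampled to 72 h in Study Design 1; no visit or sample is added. The downside is that a few profiles move out of the main steady-state summary.
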